3.3. DESIGN

Multi-centre, randomised, double blind, parallel group, feasibility study, with an embedded qualitative sub-study. Participants will be allocated to receive either: 1) intra-articular injection of anti-TNF (adalimumab 160mg) or 2) placebo injection (saline), both under ultrasound guidance. A second injection of the allocated treatment (adalimumab 80mg) or equivalent volume of placebo will be administered at 2-3 weeks. All participants will receive a physiotherapy advice leaflet providing education and advice about frozen shoulder and pain management.

Figure 1: Study flow diagram

4. METHODS - PARTICIPANTS, INTERVENTIONS AND OUTCOMES

4.1. STUDY SETTING

Participants will be recruited from at least five NHS primary-care-based musculoskeletal services and their related physiotherapy services, with treatment delivered within these services or the local secondary care site dependant on the local service provision. Participants may also be recruited from directly from NHS secondary-care-based musculoskeletal services, dependant on local service provision at sites. Musculoskeletal services treat people with a range of musculoskeletal conditions. They provide a screening, assessment and treatment service and are usually run by specialist practitioners including extended-scope physiotherapists, GPs with a specialist interest in musculoskeletal conditions, rheumatologists and orthopaedic surgeons, dependent on local service provision at site.

4.2. ELIGIBILITY CRITERIA

Adults aged 18 years and above with a new episode of shoulder pain attributable to pain-predominant stage of frozen shoulder (i.e. within approximately 3 to 9 months of onset of symptoms) diagnosed using British Elbow and Shoulder Society (BESS) guidelines and part of the NICE-accredited standards (33), who are not being considered for surgery and able to understand spoken and written English will be assessed for eligibility. Imaging, including plain radiographs, may be used to confirm a diagnosis of frozen shoulder and rule out other pathology such as glenohumeral arthritis (34) as per standard NHS care (i.e. not as part of trial procedures).

Following a diagnosis of frozen shoulder, eligibility for Anti-Freeze-F will be assessed.

4.2.1. Inclusion criteria

We will include:

- Men and women aged 18 years and above;
- With a new episode of shoulder pain attributable to pain-predominant stage of frozen shoulder (i.e. within approximately 3 to 9 months of onset of symptoms) diagnosed using criteria set out in the BESS guidelines (35) (Appendix 1);
- Who are not being considered for surgery;
- Able to understand spoken and written English;
- Willing and able to give informed consent for trial participation and comply with all study requirements and time line;

- Willing to allow his or her General Practitioner be notified of participation in the trial.
- If female, and of child-bearing potential, willing to use effective contraception throughout the treatment period and for 5 months after the last injection. See section 7.3 and 7.3.1 for definitions.

4.2.2. Exclusion criteria

We will exclude:

- Those with frozen shoulder secondary to significant shoulder trauma (e.g., dislocation, fracture or full thickness tear requiring surgery) or other causes (e.g. recent breast cancer surgery or radiotherapy);
- Those with a neurological disease affecting the shoulder;
- Those with bilateral early stage frozen shoulder;
- Those with other shoulder disorders (e.g., inflammatory arthritis, rotator cuff disorders, glenohumeral joint instability) or with red flags consistent with the criteria set out in the BESS guidelines (35);
- Those who have received corticosteroid injection for shoulder pain in the last 12 weeks to either shoulder;
- Those currently taking any anti-TNF drug;
- Those being treated with coumarin anticoagulants, such as warfarin;
- Those who have participated in another research study involving an investigational medicinal product in the past 12 weeks;
- Those with significant renal or hepatic impairment;
- Those with contra-indications to anti-TNF injection:
 - Known allergy to any anti-TNF agent or any of the excipients;
 - Known Active tuberculosis (TB) or history of TB or at risk of developing TB e.g. through the use of immunosuppressants (see below (3))
 - Known Active infection (chronic or localised) or known history of recurring infections or condition which may predispose patients to infection, including the use of concomitant immunosuppressive medications;
 - Known Moderate to severe heart failure (NYHA class III/IV);
 - Those known to have HIV, Hepatitis B or C;
 - Those at risk of Hepatitis B infection;

- Those diagnosed with Multiple Sclerosis (MS) or other central or peripheral nervous system demyelinating disorders;
- Those who have ever been diagnosed with cancer, except basal cell carcinoma (BCC);
- Those requiring live vaccination within 5 months of the last trial injection or within the 4 weeks prior to randomisation;
- Those taking biologic DMARDs;
- Females who are currently breastfeeding.
- Any other significant disease or disorder which, in the opinion of the Investigator, may either put the participants at risk because of participation in the study, or may influence the result of the study, or the participant's ability to participate in the study.

4.3. INTERVENTIONS

4.3.1. Adalimumab/Placebo Injection

Eligible participants will be allocated to receive either an intra-articular injection of adalimumab (160mg in 3.2ml for the first injection, 80mg in 1.6ml for second injection) or placebo (normal saline [0.9% NaCl] 3.2ml for the first injection and 1.6ml for the second injection). The dose of 160mg followed by 80mg two weeks later was selected as this is the approved loading dose in patients with inflammatory bowel disease. The shoulder joint capsule is vascular and we anticipate that absorption into the blood stream will follow similar kinetics as when the adalimumab is administered subcutaneously. The injection will be given into the anterior shoulder joint space in the rotator cuff interval where there is maximal inflammation of the capsule and synovium, under guided ultrasound. The injection treatment is to be given within ideally 2 weeks after randomisation by an appropriately qualified practitioner, with experience of treating frozen shoulder by ultrasound guided injection who is appropriately delegated to do so. The practitioner will be either a GP with a specialist interest in musculoskeletal conditions, rheumatologist, extended scope physiotherapist, orthopaedic surgeon, sonographer or radiologist, dependant on the local service provision at site. The practitioner will need to confirm that the participant is still in the pain predominant phase before administering the first injection. If the practitioner deems that the participant is no longer in the pain predominant phase, the participant will not receive the injection and the reason will be recorded on the trial specific injection treatment log; the participant will still be included in the 3-month follow up assessment.

If a participant has symptoms of COVID-19, tests positive for COVID-19 or is self-isolating due to government guidelines and is unable to attend for either injection, the visit will be delayed until they

receive confirmation of a negative test result or have recovered as long as they remain in the pain predominant stage. If a participant is no longer considered to be in the pain predominant stage and is unable to have the injections this will be recorded on the injection CRF and will be recorded as a withdrawn from treatment but they will continue to be followed up at 3 months.

The only means of accurately delivering the drug to the involved areas in patients with frozen shoulder is by ultrasound guidance. The skin at the site of injection of adalimumab/placebo will be infiltrated with the local anaesthetics to reduce the pain of the injection in accordance with local practice for an injection into the shoulder joint. Following administration of the local anaesthetic, there will be minimal discomfort associated with the intra-articular injection. Once adalimumab has been drawn up, it tends to lose its potency and this precludes preparation of the syringes before the patient presents for treatment. For this trial, no more than 30 minutes will elapse from when the injection is drawn up to when the injection is given.

The adalimumab/placebo will typically be delivered using a syringe fitted with typically a 21 gauge needle or greater. All participants irrespective of whether they are still in the pain predominant phase, will receive a second injection (adalimumab/placebo) administered 2-3 weeks after the first injection, unless the participant declines the second injection. The reason will be recorded on the trial specific injection treatment log and the participant will still be included in the 3-month follow up assessment. Participants will be advised to continue with their physiotherapy and resume normal activities immediately after the injection. Participants will be provided with a written information leaflet advising them that there will be no restriction on their activities after the injection and what to do if they experience any side effects. Each patient will receive a maximum of two injections, either adalimumab or placebo. Injection details, including time from randomisation to injection delivery, will be recorded on a trial specific injection treatment log. A second injection will not be administered if any related grade 3 or above Adverse Event as per the Common Terminology Criteria for Adverse Events (CTCAE) v5.0 occur following the first injection, or if the patient tests positive for TB or hepatitis B surface antigen.

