4.3.1.2 Supply and Storage of IMPs

Participating sites are to procure adalimumab (Idacio from Fresenius Kabi) (40mg / 0.8 ml vials) and normal saline (0.9% NaCl). The adalimumab must be stored in a refrigerator (2°C – 8°C) and must not be frozen. The vial should be kept in the outer carton in order to protect from light, it may be stored at temperatures up to a maximum of 25°C for a period of up to 14 days. Sites need to ensure that they procure the adalimumab from Fresenius Kabi in vials rather than a pre-filled syringe or pen. The needles fitted to the pre-filled syringes is too short for shoulder joint injection. Fresenius Kabi is the only company that supplies the adalimumab in vials. Use of this product will avoid the necessity to transfer the IMP from the pre-filled syringe to another syringe before injection. The cost of IMP purchase for the trial will be reimbursed by the Sponsor. Funding for purchase of the adalimumab and placebo will be provided by 180 Life Sciences. The IMP will be dispensed upon receipt of a trial-specific prescription. Where the IMP is collected from pharmacy/handled by staff who are blinded to treatment the IMP packaging will be obscured, in a sealed opaque plastic bag. Specific instructions that will cover the importance of keeping the IMP blinded will be provided at the Site Initiation Visit as it is not always possible for unblinded staff to collect the IMP from pharmacy. Trial-specific dispensing logs are required to be maintained. Trial-specific accountability for bulk receipt and returns/destruction will be required. There will be no provision of the IMP after the trial period.

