5.2. BLINDING

Study participants will be blinded to their treatment allocation. The clinician delivering the treatment injection will not be blinded to the treatment allocation as they will be required to prepare and administer the IMP. They will not be involved with any further trial-specific assessment of the participant. They will be educated on the importance of maintaining the blind of both study participants and the rest of the site staff. All other site staff, except pharmacy staff, will be blinded. The clinician assessed outcomes at the 3 month follow-up clinic visit will be undertaken by a blinded member of the clinical team at site. The trial statistician, Trial Office staff member undertaking checks of dispensed medication, and data entry personnel will not be blinded to the treatment allocation. The remaining members of the trial management team, including the staff conducting the qualitative interviews will be blinded to treatment allocation until after the data analysis is complete.

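### The first injection can be withheld after randomisation on a stage judgement by an unblinded practitioner, and nothing requires that judgement before the allocation is known

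*Combined protocol and SAP*

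**What the plan says.** Four parts of the protocol bear on this point.

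- **Timing.** The participant timeline (4.5) and the schedule of procedures (Appendix 2) put randomisation at screening and the first injection at a later visit. Section 4.3.1 says: "The injection treatment is to be given within ideally 2 weeks after randomisation by an appropriately qualified practitioner".
- **The decision.** At that visit, "The practitioner will need to confirm that the participant is still in the pain predominant phase before administering the first injection". The consequence is explicit: "If the practitioner deems that the participant is no longer in the pain predominant phase, the participant will not receive the injection". The reason goes on the injection treatment log and the participant stays in the 3-month follow-up. The COVID-19 paragraph of the same section also makes a delayed injection conditional on stage, without naming who judges it.
- **Who decides.** Section 5.2 says: "The clinician delivering the treatment injection will not be blinded to the treatment allocation as they will be required to prepare and administer the IMP". It then limits that person's later role: "They will not be involved with any further trial-specific assessment of the participant".
- **What depends on delivery.** Practicality of delivery, including time to first injection, is a primary objective (3.2). The share of participants given the first injection as randomised and in time is one of three progression criteria (Table 4, section 6.5): Green at 75% or more, Amber from 50%, Red below 50%. Table 4 does not split it by arm.

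**The concern.** The stage check is a matter of judgement. Section 3.1.1 describes the phases as overlapping, and the eligibility criteria give the painful stage only as an approximate span of months. No criteria are set for the check at the injection visit. In a borderline case, a clinician who knows whether the syringe will hold an off-label biologic or saline may lean one way or the other, without intending to.

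If that happened, three results would be affected: first-injection delivery in each arm, which is a feasibility result in its own right; the treatment difference at 3 months, because the arms would differ in how many people were injected at all; and the signal in range of motion that section 6.5 says will also inform the decision to progress.

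**Working it through.** **Step 1: do the safeguards reach this decision?**

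- Intention-to-treat analysis (6.3) and continued follow-up (4.3.1) prevent exclusion from the analysis. They do not equalise delivery.
- Blinding of the participant and of the 3-month assessor (5.2) protects outcome measurement. It does not cover the choice to inject.
- The bar on the injector in 5.2 concerns further assessments. The stage check comes before the injection.
- The log review in 7.4 checks that participants receive the drug they were allocated. It does not test whether a reason for withholding was independent of allocation.
- The second injection is given irrespective of stage (4.3.1), apart from the COVID-19 paragraph. The point therefore concerns mainly the first injection.

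No section gives the stage check to blinded staff or requires it to be recorded before the allocation is known. Nor does any section say when the injector learns the allocation: 5.1 describes the randomisation service but not who at the site sees the result, or when.

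**Step 2: size of an arm.** Section 5.5 gives 84 participants. This reproduces as 0.30 × 280 = 84, and 70 / (1 − 0.15) = 82.4, rounded up to 83, is one below it. At 1:1 (5.1), each arm has 84 / 2 = 42.

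**Step 3: illustration.** The documents give no withholding rate, so the excess *f* in one arm is assumed to be 5 to 15 percentage points.

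- Participants affected: 42 × 0.05 = 2.1 to 42 × 0.15 = 6.3.
- Fall in the pooled rate: 2.1 / 84 = 2.5 points to 6.3 / 84 = 7.5 points, which is half the one-arm excess.
- Effect on the Green line: a fall of 2.5 points takes delivery below 75% only if it would otherwise be below 75 + 2.5 = 77.5%. For a fall of 7.5 points the limit is 75 + 7.5 = 82.5%.
- Effect on the drug estimate, if the excess is in the adalimumab arm and those participants receive no drug and gain no benefit: the intention-to-treat effect becomes (1 − *f*) times the full effect, that is 95% to 85% of it.
- If the excess is in the saline arm, that formula does not apply. Part of the comparator becomes no injection in place of a blinded saline injection.

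**Step 4: would the planned figures show it?** These are assumed counts with Wald 95% intervals for the difference.

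| Injected, of 42 per arm | Pooled | Difference (95% CI) |
|---|---|---|
| 40 and 38 | 92.9% | 4.8 points (−6.2 to 15.7) |
| 40 and 34 | 88.1% | 14.3 points (0.8 to 27.8) |
| 42 and 21 | 75.0% | 50.0 points (34.9 to 65.1) |

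The last row is an arithmetic limit, not a forecast: a pooled Green says nothing about balance between arms. The first row shows that by-arm reporting alone could not rule out a small imbalance. The order of events at the visit is therefore the main protection.

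**The case against.** The strongest reply is that the practitioner may not know the allocation when judging stage. Section 5.2 ties the unblinding to preparing and giving the product. Section 4.3.1 says of the drug's loss of potency once drawn up that "this precludes preparation of the syringes before the patient presents for treatment", and 4.3.1.3 places preparation in a separate area. A site could well check stage first and open the product afterwards. This stands as far as it goes. A reader might infer from 5.2 that the decision is made with the allocation known, but the documents do not say so. Equally, they do not require the reverse order, and drawing up late does not show that the allocation is learned late.

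A reader might also infer that the delivery criterion could be turned into a false Green. It could not. A withheld injection is truly undelivered, so extra withholding only lowers the pooled rate, and Green refers to the current procedures, which include this check.

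Nor does dilution follow whichever arm is affected; it applies to withheld adalimumab only. Section 6.3 adds that the effect estimate is not powered to be definitive.

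The assumed range has no anchor in the documents. With injection ideally within 2 weeks of randomisation and a painful phase described as lasting 3 to 9 months, few participants may change stage in the interval. A 15-point difference would then be large.

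The packaging provision is not a ready answer: "the IMP packaging will be obscured, in a sealed opaque plastic bag" applies where blinded staff collect or handle the product, and is not described as hiding the allocation from the injector.

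Finally, some reporting may already be intended. Section 6.3 lists delivery of the intervention and ends with figures per group and overall for the second injection. Whether that bracket covers the earlier items is unclear.

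**Conclusion.** The point holds as an unprotected step, not as a demonstrated bias. Two facts are explicit: stage is judged after randomisation and decides the first injection, and the clinician who judges it is not blinded. The gap is that nothing places the judgement before knowledge of the allocation, so withholding could differ by arm for reasons linked to allocation.

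The documents do not show that this will happen, or how often injections will be withheld at all. Under the assumed excess, about 2 to 6 participants are affected. The progression result changes only if delivery would otherwise lie close above the Green line. The 5% to 15% loss of drug effect needs the excess to be in the adalimumab arm and no benefit in those left untreated. The consequence is modest for a feasibility study, but the protection is cheap.

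**What to change.** In 4.3.1 and 5.2, require the practitioner to make, sign and time the stage confirmation on the injection log before learning the allocation: before the product is opened or prepared and before any document that reveals the allocation is seen. Apply the same order to a first injection delayed under the COVID-19 paragraph.

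In 6.3, state that first-injection delivery, and first injections withheld because the participant is no longer pain-predominant, will be reported by arm and overall.

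The clinical rule does not change, and the check stays with the practitioner to whom 4.3.1 assigns it. The cost is a sentence in the protocol, one time field on an existing log and a line in the statistical methods. The downside is a minor change to the visit workflow: sites must keep the allocation from the injector until the check is logged, including where the injector would otherwise see the prescription or collect the product. Label: cheap improvement.

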4.3.1.1 IMP Description

Adalimumab is a human monoclonal antibody with Marketing Authorisation but will be used off-label for this trial.

Normal saline (0.9% NaCl) will be used as the placebo.

4.3.1.2 Supply and Storage of IMPs

Participating sites are to procure adalimumab (Idacio from Fresenius Kabi) (40mg / 0.8 ml vials) and normal saline (0.9% NaCl). The adalimumab must be stored in a refrigerator (2°C – 8°C) and must not be frozen. The vial should be kept in the outer carton in order to protect from light, it may be stored at temperatures up to a maximum of 25°C for a period of up to 14 days. Sites need to ensure that they procure the adalimumab from Fresenius Kabi in vials rather than a pre-filled syringe or pen. The needles fitted to the pre-filled syringes is too short for shoulder joint injection. Fresenius Kabi is the only company that supplies the adalimumab in vials. Use of this product will avoid the necessity to transfer the IMP from the pre-filled syringe to another syringe before injection. The cost of IMP purchase for the trial will be reimbursed by the Sponsor. Funding for purchase of the adalimumab and placebo will be provided by 180 Life Sciences. The IMP will be dispensed upon receipt of a trial-specific prescription. Where the IMP is collected from pharmacy/handled by staff who are blinded to treatment the IMP packaging will be obscured, in a sealed opaque plastic bag. Specific instructions that will cover the importance of keeping the IMP blinded will be provided at the Site Initiation Visit as it is not always possible for unblinded staff to collect the IMP from pharmacy. Trial-specific dispensing logs are required to be maintained. Trial-specific accountability for bulk receipt and returns/destruction will be required. There will be no provision of the IMP after the trial period.

4.3.1.3 Preparation and labelling of IMPs

A trial-specific annex 13 compliant label will be applied to the IMP prior to dispensing under the Regulation 37 exemption. Preparation of the IMP needs to occur in a clinic room/area separate from the participant to ensure the participant remains blinded to their treatment allocation immediately prior to injection.

Adalimumab:

The adalimumab, 160mg in 3.2ml or 80mg in 1.6ml, will be drawn up from the vials.

Normal saline:

3.2ml or 1.6 ml of saline (0.9% NaCl) will be drawn up.

Both the IMP and placebo have a similar viscosity and appearance so that the two treatments, adalimumab or saline, will be indistinguishable. The same type of syringe and needle will be used for injection of both adalimumab and saline thus maintaining the blinding of the participant and staff not involved in preparation or administering the IMP.

